1.8 CIPN endpoint measurement tools

Given that this is a pilot trial, we will evaluate neuropathy with a variety of patient-reported outcome (PRO) tools. (See [Section 11.1](#))

1.9 Toxicity and QOL Endpoint Measurement Tools

We will utilize the symptom experience diary ([Appendix V](#)) and CTCAE version 5.0 criteria to look for any evidence of toxicity from PEA, understanding that substantial past work has suggested that this product does not cause any significant toxicity. This questionnaire will also evaluate QOL changes. (See Sections [11.2](#) and [11.3](#) for a detailed description of the measurement tools)

2.0 Goals

2.1 Primary

The primary objective is to look for evidence of the efficacy of PEA at two different doses relative to placebo responses, as a treatment for CIPN. This is being done to

inform the design of a subsequent phase III trial of PEA for treating bothersome established CIPN.

2.2 Secondary

- 2.2.1 To assess the safety of PEA at the two study doses.
- 2.2.2 To evaluate changes in patient-reported quality of life from baseline to the end of 8 weeks.

2.3 Exploratory

- 2.3.1 To explore whether PEA appears to affect cognition in the study patients.
- 2.3.2 To explore the weekly trajectory of CIPN from baseline to 8 weeks.
- 2.3.3 To explore the weekly trajectory of pain using the single-item numerical rating scale from baseline to 8 weeks.
- 2.3.4 To explore the weekly patient global impression of change in each treatment arm from baseline to 8 weeks.
- 2.3.5 To explore the weekly chemotherapy induced peripheral neuropathy in each treatment arm from baseline to 8 weeks.
- 2.3.6 To explore the PEA effects on CIPN20 between two PEA dosage arms.
- 2.3.7 To explore the number of recurrent cancer events by study arm
- 2.3.8 To explore the overall survival by study arm

3.0 Patient Eligibility

NOTE: Waivers to eligibility criteria are not allowed per ACCRU policy

3.1 Registration -- Inclusion Criteria

- 3.1.1 Age \geq 18 years.
- 3.1.2 ECOG Performance Status 0, 1, 2 (Form available on ACCRU website).
NOTE: Patients with a history of metastatic cancer or an ECOG Performance Status of 2 must have lab work (see Section 3.1.9) completed \leq 28 days prior to registration.
- 3.1.3 Pain, numbness, tingling or other symptoms of CIPN of \geq 3 months (90 days) duration for which the patient is seeking an intervention.
- 3.1.4 Neurotoxic chemotherapy must have been completed \geq 3 months (90 days) prior to registration and there must be no further planned neurotoxic chemotherapy for $>$ 2 months after registration.
Note: The study is limited to those with taxane- and/or platinum-based neuropathy.
- 3.1.5 Patient must note tingling, numbness or pain symptoms of at least a four out of ten \leq 7 days prior to registration.
Note: On a 0-10 scale where zero was 'no problem' and ten being 'as bad a problem that could be imagined': *how much of a problem has numbness, tingling,*

and/or pain in your fingers and/or toes been in the past week? (patient verbal report utilizing question 1 in [Appendix VI “Peripheral Neuropathy Questions”](#)).

- 3.1.6 Patient must be able to speak, read and comprehend English.
- 3.1.7 For women of childbearing potential only, a negative urine or serum pregnancy test done \leq 14 days prior to registration is required.
A female of childbearing potential is a sexually mature female who: 1) has not undergone a hysterectomy or bilateral oophorectomy; or 2) has not been naturally postmenopausal for at least 12 consecutive months (i.e., has had menses at any time in the preceding 12 consecutive months).

NOTE: If the urine test cannot be confirmed as negative, a serum pregnancy test will be required.

- 3.1.8 Life expectancy \geq 6 months.
- 3.1.9 Required Initial Laboratory Values: Following completion of chemotherapy, patients must have had a CBC and serum chemistries, including the following:
 - Platelet count $> 100,000/\text{mm}^3$
 - Absolute neutrophil count (ANC) $\geq 1,000/\text{mm}^3$
 - Hemoglobin $> 11 \text{ g/dL}$
 - Serum transaminase [ALT or AST] $\leq 1.2 \times$ upper limit of normal (ULN)
 - Alkaline phosphatase $\leq 1.2 \times$ ULN
 - Serum creatinine $\leq 1.2 \times$ ULN

NOTE: Patients with a history of metastatic cancer or an ECOG Performance Status of 2 must have these labs completed \leq 28 days prior to registration.

- 3.1.10 Able to swallow oral medication.
- 3.1.11 Provide written informed consent \leq 28 days prior to registration.

3.2 Registration – Exclusion Criteria

- 3.2.1 Currently receiving neurotoxic chemotherapy for a second cancer or recurrence of the primary cancer.
- 3.2.2 Impaired decision-making capacity (such as with a diagnosis of dementia or memory loss).
- 3.2.3 Evidence of residual cancer, per routine clinical practice-based parameters.
- 3.2.4 Comorbid conditions:
 - a) Previous diagnosis of diabetic or another non chemotherapy induced peripheral neuropathy.
 - b) Previous history of peripheral neuropathy prior to receiving neurotoxic chemotherapy.
 - c) Neuropathy from HIV infection. Note: Patients with HIV infections are eligible as long as they do not have a neuropathy from their viral illness.

- 3.2.5 Concurrent use of a cannabis product (THC and/or CBD). Patients should have discontinued these products \geq 4 weeks prior to registration.
- 3.2.6 Current or previous use of PEA.
- 3.2.7 Currently receiving or planning to start any of the following agents: opioids, duloxetine, gabapentin or pregabalin. Patients are eligible if they discontinue these medications \geq 1 week prior to registration.
- 3.2.8 Any of the following because the study involves an investigational agent whose genotoxic, mutagenic, and teratogenic effects on the developing fetus and newborn are unknown:
 - Pregnant persons
 - Nursing persons
 - Persons of childbearing potential who are unwilling to employ adequate contraception

4.0 Test Schedule

	Screening			Active Monitoring Phase	
	Prior to Registration			Prior to Start of Treatment (baseline)	End of each weekly cycle (for 8 weeks)
	≤ 28 Days	≤ 14 Days	≤ 7 Days		
Tests & Observations					
History	X				
CBC and serum chemistries, including serum transaminase [ALT or AST], alkaline phosphatase and Cr ¹	X ¹				
ECOG PS	X				
Laboratory Studies					
Serum or Urine HCG ²		X ²			
Patient reported measures**					
EORTC QLQ-CIPN 20 (Appendix II)				X	X
Patient Global Impression of Change (Appendix III)					X
Chemotherapy-Induced Peripheral Neuropathy Assessment Tool (Appendix IV)				X	X

Symptom experience diary (Appendix V)				X	X
Peripheral Neuropathy Question (Appendix VI)			X ⁴	X	X
Cognitive Functioning Assessment (Appendix VII)				X	X
Adverse Event Assessment ³					X ³
Nurse telephone contact ³ (Appendix VIII)					X ³

** To be completed using paper booklets. Patient questionnaire booklets are to be available prior to the registration of any patients. The booklet order form is located on the ACCRU website under 'Manuals and Forms'. Patients are to complete these booklets prior to the end of each week of treatment (See Section 7.2). See appropriate Appendices for samples of the booklets.

1 This blood testing is required within the 28 days prior to registration if the patient has a history of metastatic cancer or currently has an ECOG Performance Score of 2 (See eligibility criteria 3.1.9). For patients who do not have a history of metastatic cancer or a current ECOG Performance Score of 2, this blood testing is to have been completed after the patient finished their chemotherapy per eligibility criteria 3.1.4.

2 For women of childbearing potential. Must be done \leq 14 days prior to registration.

3 Nurse/Research Coordinator will contact the patient at the end of each weekly cycle (+ 2 days) to remind the patient to complete questionnaires, answer questions, and to query adverse events.

4 To be collected orally (per eligibility criteria 3.1.5) and the response will be documented on the eligibility checklist and in the clinic note (per section 18.5).

4.1 Survival Follow-up

After completing 8 weeks of treatment, patients will proceed to survival follow-up. A Nurse/Research Coordinator will contact the patient to inquire about neuropathy status, disease status, and survival at both 6 months (\pm 30 days) and 12 months (\pm 30 days) after registration. There will be no additional follow-up after these two timepoints. ([Appendix IX](#))

5.0 Stratification Factors:

- Gender: Male vs Female
- Prior Chemotherapy Received: Any **Taxane** ± **carboplatin** ± other agents versus **Oxaliplatin** based versus **other** (never received a taxane nor oxaliplatin)

6.0 Registration/Randomization Procedures

6.1 Site Procedures

6.1.1 Study staff will need to complete the required training prior to gaining access to the registration application. This is located on the ACCRU web page at [REDACTED] Refer to Study Resources → Applications. Near the bottom of the page there will be a link to the “Research Registration Application Training.” After training is complete, study staff must complete the “Attestation of Training” and send to the ACCRU Registration Office at [REDACTED]

6.1.2 Documentation of IRB approval must be on file in the Registration Office before an investigator may register any patients. Approvals should be uploaded using Florence online.

In addition to submitting initial IRB approval documents, ongoing IRB approval documentation must be on file (no less than annually) with ACCRU. Approvals should be uploaded using the Florence online. If the necessary documentation is not submitted in advance of attempting patient registration, the randomization will not be accepted and the patient may not be enrolled in the protocol until the situation is resolved.

Submission of annual IRB approvals is required until the study has been closed through your IRB.

6.2 Registration Procedures

6.2.1 To register a patient, access the ACCRU web page at [REDACTED] go to the Study Resources → Application section and click on “Registration” and enter the registration application. The registration application is available 24 hours a day, 7 days a week. Back up and/or system support contact information is available on the Web site. If unable to access the Web site, email the Academic and Community Cancer Research United (ACCRU) Registration Office at [REDACTED] between the hours of 8 a.m. and 4:30 p.m. Central Time (Monday through Friday).

Instructions for the registration application are available on the above web page under the Study Resources → Application section. Please refer to the “Research Registration Application Training” or Quick Reference Guide for instructions.

Prior to initiation of protocol treatment, this process must be completed in its entirety and an ACCRU subject ID number must be available as noted in the instructions. It is the responsibility of the individual and institution registering the patient to confirm the process has been successfully completed prior to release of the study agent.

Patient registration via the registration application can be confirmed in any of the following ways:

- Contact the ACCRU Registration Officer [REDACTED] If the patient was fully registered, the ACCRU Registration Office staff can access the information from the centralized database and confirm the registration.
- Refer to the Research Registration Application training on the ACCRU website under Study Resources → Applications.

6.2.2 Prior to accepting the registration/randomization, the registration/randomization application will verify the following:

- IRB approval at the registering institution
- Patient eligibility
- Existence of a signed consent form
- Existence of a signed authorization for use and disclosure of protected health information

6.2.3 Treatment cannot begin prior to registration and must begin \leq 14 days after registration.

6.2.4 Pretreatment tests/procedures (see Section 4.0) must be completed within the guidelines specified on the test schedule.

6.2.5 Treatment on this protocol must commence at an ACCRU institution under the supervision of an oncologist.

6.2.6 Study drug is available on site.

6.2.7 Patient questionnaire booklet is available on site.

6.3 Randomization Procedures

6.3.1 The factors defined in Section 5.0 will be used as stratification factors.

6.3.2 After the patient has been registered into the study, the values of the stratification factors will be recorded, and the patient will be assigned to one of the following treatment groups using the Pocock and Simon dynamic allocation procedure which balances the marginal distributions of the stratification factors between the treatment groups [105].

- Palmitoylethanolamide: 400 mg (1 capsule daily) PO for 8 weeks
- Palmitoylethanolamide: 800 mg (1 400mg capsule twice daily) PO for 8 weeks

- Placebo: 1 capsule PO daily for 8 weeks
- Placebo: 1 capsule PO twice daily for 8 weeks

6.4 Procedures for Double-Blinding the Treatment Assignment

6.4.1 After the treatment assignment has been ascertained by the registration/randomization application, the registration specialist will notify the designated unblinded data manager/nurse/pharmacist at the patient's institution. The name of this contact person is to be entered in the designated space on the eligibility checklist, so the Registration Office personnel have it for each patient at the time of randomization. Make sure this contact person will be available at the time of randomization so he or she can take a call from the registration specialist if necessary. This contact person may not be involved in assessing adverse events or any other outcome measure and should not be the same person listed on page one of the Eligibility Checklist Form as the person completing the form. The last page of the Eligibility Checklist Form should provide the e-mail address and the appropriate contact information (including phone number). The registration specialist will then communicate the treatment assignment to the designated contact at the patient's institution.

6.4.2 The treatment assignment will be to palmitoylethanolamide 400 mg once daily, palmitoylethanolamide 400 mg twice daily, placebo once daily, or placebo twice daily. Innexus Nutraceuticals will provide supplies labeled for investigational use to McKesson Specialty Pharmacy's Clinical Research Services. Each participating institution will order the drug from McKesson using the protocol-specific Drug Order Request Form. Each participating institution will be responsible for monitoring drug supplies and will use the Drug Order Request Form to order additional supplies as needed. Upon receipt of orders, McKesson Specialty Pharmacy's Clinical Research Services will send bulk supply to participating institutions. The palmitoylethanolamide/placebo drug supplies will be prepared and labeled by the unblinded pharmacist per Section 7.1 so that the contents are not discernible to the person administering the treatment.

6.4.3 The unblinded pharmacist will maintain records that indicate the identity of the patient and their corresponding treatment assignment.

7.0 Treatment Plan/Intervention

Protocol treatment is to begin \leq 14 days of registration.

This is a randomized double-blind trial. See Section 15.1 for drug procurement instructions.

Patients with peripheral neuropathy either from a platinum or taxane based chemotherapy will be randomized if eligible to one of four treatment arms:

Agent	Dose	Route	Day
Palmitoylethanolamide (PEA)	400 mg (1 capsule daily)	PO	Daily for 8 weeks
Palmitoylethanolamide (PEA)	800 mg (1 400 mg capsule twice daily)	PO	Daily for 8 weeks
Placebo	1 capsule daily	PO	Daily for 8 weeks
Placebo	1 capsule twice daily	PO	Daily for 8 weeks

Medications will be taken once or twice daily depending on randomization. Assessment of neuropathy, side effects and cognitive function will occur weekly.

7.1 Palmitoylethanolamide (PEA)/Placebo

Beginning on Day 1 of the study, and for eight weeks, patients will be instructed to take one of the following:

- Palmitoylethanolamide (400 mg) or placebo: 1 capsule by mouth once in the morning daily for 8 weeks

OR

- Palmitoylethanolamide (400 mg) or placebo: 1 capsule by mouth once in the morning and once in the evening daily for 8 weeks

7.2 Submission of Patient Completed Measures (Booklets)

Patient-completed questionnaire booklets for this study are to be ordered prior to the registration of any patients. The booklet order form is located on the ACCRU website under 'Manuals and Forms. Samples of questionnaire booklets are available in Appendices II-VII for reference and IRB submission only. Booklets must be given to patients to complete and patients should be instructed to return the booklets to site staff either in person or by mail and site staff will enter patient responses into Medidata Rave. At visits in which booklets are to be completed, the booklet should be given to and completed by the patient before any discussion of the patient's health status or test results. The PRO submission schedule is provided in the Study Calendar.

Baseline Booklet: The baseline questionnaire booklet should be completed in clinic on the same day as registration and returned to study staff. In the event the patient is unable to complete while in the clinic, the patient may complete at home and return by mail prior to starting the study medication.

Weekly Booklets: Questionnaire booklet(s) will be provided to patients to complete at home on a weekly basis for a total of eight weeks. Before the booklets are given to the patients, the nurse/study assistant will label each booklet with the week number and the anticipated 7-day weekly cycle start dates, in chronological order. Patients should be instructed to return the booklets by mail weekly. If, by chance, the patient has a regularly scheduled clinic visit at any time during the study period, the patient could return that

week's questionnaire during the clinic visit. Institutions must provide patients with sufficient self-addressed stamped envelopes for this purpose. Site staff will enter patient responses into Rave upon receipt of the completed booklets.

Verbal administration of the measures for visually impaired patients is permitted if the measure and verbal administration of the measure is conducted in a language understandable to the patients.

7.3 Unblinding Procedures

Unblinding during active study treatment can be done only in cases of an emergency. Follow the directions below to unblind patient treatment. Please note that if a treatment assignment is unblinded, the patient must discontinue protocol therapy.

7.3.1 Emergency Unblinding Procedures

Examples of emergencies include 1) a life-threatening unexpected adverse event that is at least possibly related to the investigational agent and for which unblinding would influence treatment decisions; or 2) medication error, such as accidental overdose.

In the event of an emergency, email the ACCRU Registration Office at [REDACTED] to break the code on Monday through Friday, 8:00 a.m. to 4:30 p.m. Central Time. If the code must be broken after hours, assume the patient was assigned to active treatment and treat accordingly. Send an email to the ACCRU Registration Office informing them of the need to un-blind a patient. Provide your contact information so that ACCRU Registration Office personnel can respond to the email the next business day.

7.3.2 Study Completion Unblinding

On a case by case basis, if in the judgement of the treating physician, it would be helpful for the future clinical care of the individual patient, the code may be broken *after* the patient has completed the study. That is, after the patient has completed study treatment and mailed in all of the required study questionnaires. The ACCRU Registration Office may be contacted to find out which study therapy the patient was receiving. This would allow for the individual patients to choose whether to continue taking active PEA or to start it. This treatment would be considered off study and patients should discuss with their primary cancer physician. Patients would need to purchase palmitoylethanolamide on their own terms.

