10.3.1 Death

- Any death occurring within 30 days of the last dose, regardless of attribution to an agent/intervention under an IND/IDE requires expedited reporting within 24-hours.
- Any death occurring greater than 30 days with an attribution of possible, probable, or definite to an agent/intervention under an IND/IDE requires expedited reporting within 24-hours.

• Reportable categories of Death

- Death attributable to a CTCAE term.
- Death Neonatal: A disorder characterized by cessation of

life during the first 28 days of life.

- Death NOS: A cessation of life that cannot be attributed to a CTCAE term associated with Grade 5.
- Sudden death NOS: A sudden (defined as instant or within one hour of the onset of symptoms) or an unobserved cessation of life that cannot be attributed to a CTCAE term associated with Grade 5.
- Death due to progressive disease that cannot be attributed to a CTCAE term associated with Grade 5 should be reported as **Grade 5 “Disease progression”** under the system organ class (SOC) of General Disorders and Administration Site Conditions. Evidence that the death was a manifestation of underlying disease (e.g., radiological changes suggesting tumor growth or progression; clinical deterioration associated with a disease process) should be submitted.

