10.4 Expedited Adverse Event Reporting Requirements for IND/IDE Agents

10.4.1 Late Phase 2 and Phase 3 Studies: Expedited Reporting Requirements for Adverse Events that Occur on Studies under an IND/IDE within 30 Days of the Last Administration of the Investigational Agent/Intervention^{1,2}

FDA REPORTING REQUIREMENTS FOR SERIOUS ADVERSE EVENTS (21 CFR Part 312)

NOTE: Investigators **MUST** immediately report to the sponsor (NCI) **ANY** Serious Adverse Events, whether or not they are considered related to the investigational agent(s)/intervention (21 CFR 312.64)

An adverse event is considered serious if it results in **ANY** of the following outcomes:

- 1) Death
- 2) A life-threatening adverse event
- 3) An adverse event that results in inpatient hospitalization or prolongation of existing hospitalization for ≥ 24 hours
- 4) A persistent or significant incapacity or substantial disruption of the ability to conduct normal life functions
- 5) A congenital anomaly/birth defect.
- 6) Important Medical Events (IME) that may not result in death, be life threatening, or require hospitalization may be considered serious when, based upon medical judgment, they may jeopardize the patient or subject and may require medical or surgical intervention to prevent one of the outcomes listed in this definition. (FDA, 21 CFR 312.32; ICH E2A and ICH E6).

ALL SERIOUS adverse events that meet the above criteria **MUST** be immediately reported to the NCI via electronic submission within the timeframes detailed in the table below.

Hospitalization	Grade 1 Timeframes	Grade 2 Timeframes	Grade 3 Timeframes	Grade 4 & 5 Timeframes
Resulting in Hospitalization ≥ 24 hrs		10 Calendar Days		24-Hour 5 Calendar Days
Not resulting in Hospitalization ≥ 24 hrs	Not required		10 Calendar Days	

NOTE: Protocol specific exceptions to expedited reporting of serious adverse events are found in the Specific Protocol Exceptions to Expedited Reporting (SPEER) portion of the CAEPR

Expedited AE reporting timelines are defined as:

- “24-Hour; 5 Calendar Days” - The AE must initially be submitted electronically within 24 hours of learning of the AE, followed by a complete expedited report within 5 calendar days of the initial 24-hour report.
- “10 Calendar Days” - A complete expedited report on the AE must be submitted electronically within 10 calendar days of learning of the AE.

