¹Serious adverse events that occur more than 30 days after the last administration of investigational agent/intervention and have an attribution of possible, probable, or definite require reporting as follows:

Expedited 24-hour notification followed by complete report within 5 calendar days for:

- All Grade 4, and Grade 5 AEs

Expedited 10 calendar day reports for:

- Grade 2 adverse events resulting in hospitalization or prolongation of hospitalization
- Grade 3 adverse events

²For studies using PET or SPECT IND agents, the AE reporting period is limited to 10 radioactive half-lives, rounded UP to the nearest whole day, after the agent/intervention was last administered. Footnote “1” above applies after this reporting period.

Effective Date: May 5, 2011

Special Instructions:

- Follow site-specific reporting guidelines.
- Submit the ACCRU Adverse Event Expedited Report Form to the ACCRU SAE Coordinator via email [REDACTED]. The ACCRU SAE Coordinator will forward to [REDACTED] via email: [REDACTED]
- The ACCRU IND Coordinator will assist the sponsor-investigator in notifying the FDA if required.

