10.5.2 Baseline and Adverse Events Evaluations

Not applicable.

10.5.3 Submit via appropriate Academic and Community Cancer Research United (ACCRU) Case Report Forms (i.e., paper or electronic, as applicable) the following AEs experienced by a patient and not specified in Section 10.5:

10.5.3.1 Grade 1 and 2 AEs deemed *possibly, probably, or definitely* related to the study treatment or procedure.

10.5.3.2 Grade 3 and 4 AEs regardless of attribution to the study treatment or procedure

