16.6 Study Monitoring

16.6.1 Adverse Event Stopping Rule

The stopping rule specified below is based on the knowledge available at study development. We note that the Adverse Event Stopping Rule may be adjusted in the event of either (1) the study re-opening to accrual or (2) at any time during the conduct of the trial and in consideration of newly acquired information regarding the adverse event profile of the treatment(s) under investigation. The study team may choose to suspend accrual because of unexpected adverse event profiles that have not crossed the specified rule below.

Accrual will be temporarily suspended to this study if at any time we observe events considered at least possibly related to study treatment (i.e., an adverse event with attribute specified as “possible”, “probable”, or “definite”) that satisfy the following:

- If 2 or more patients in the first 10 treated patients in any study arm (or 20% of all patients after 10 are accrued) experience a grade 3 or higher adverse event and the event rate is higher in the active treatment arm.

We note that we will review grade 4 and 5 adverse events deemed “unrelated” or “unlikely to be related”, to verify their attribution and to monitor the emergence of a previously unrecognized treatment-related adverse event.

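### Section 7.3.2 allows a non-emergency code break before adverse events have been graded and attributed, which exposes a limited set of attribution-dependent safety records

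*Combined protocol and SAP*

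**What the plan says.** Section 7.3.2 permits unblinding outside emergencies "On a case by case basis, if in the judgement of the treating physician" it would help the patient's future care. The only timing condition is that it comes "after the patient has completed study treatment and mailed in all of the required study questionnaires". The stated purpose is practical: "This would allow for the individual patients to choose whether to continue taking active PEA or to start it".

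Two other sections treat knowledge of the arm more strictly. Section 6.4.1 says that the site's unblinded contact may not assess adverse events or other outcomes. Section 8.1 wants a decision to stop treatment for a suspected adverse event taken before the code is opened. Section 7.3.2 has no matching condition for attribution.

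Attribution matters in four places:
- Section 10.5.3.1 limits routine submission of low-grade events to "Grade 1 and 2 AEs deemed" related to treatment.
- Footnote 1 to the table in Section 10.4.1 covers serious events more than 30 days after the last dose, which must "have an attribution of possible, probable, or definite require reporting as follows".
- Section 10.3.1 asks for an expedited report of "Any death occurring greater than 30 days with an attribution of possible, probable, or definite", and Section 10.5.3.3.2 applies the same condition to grade 5 submission.
- The suspension rule in Section 16.6.1 counts only "events considered at least possibly related to study treatment".

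**The concern.** Attribution is a blinded judgement only while the code is closed. Once a physician knows that the patient took placebo, there is little basis for calling an event related to PEA; one who knows that the patient took PEA can still do so. Where a record exists or is counted only if the event is judged related, the same event may then be handled differently by arm. The direction is predictable: PEA would look worse relative to placebo.

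At stake are the descriptive adverse event summary under the secondary safety objective (2.2.1), the operation of the suspension rule during accrual, and late safety reports. The low-grade summary has some weight here, because Section 15.1.7 lists gastrointestinal upset and drowsiness among the infrequent effects reported with PEA.

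**Working it through.** The plan gives no figure for this exposure, so the check sets the rules side by side and works out the timing.

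**Timing.** Treatment lasts 8 × 7 = 56 days. The 30-day window therefore closes on day 56 + 30 = 86, counted from the first dose. Treatment may start up to 14 days after registration (6.2.3), so counted from registration the last dose falls on days 56 to 70 and the window closes on days 86 to 100. The 6-month call (Section 4.1) falls at 182.6 ± 30, or about days 153 to 213 from registration. A code break can therefore come up to about 30 days before the window closes, and well before the next scheduled contact. Section 7.3.2 also does not tie it to the week-8 adverse event call, which may take place up to 2 days after the cycle ends (Section 4.0, note 3).

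**What depends on attribution.**

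| Record | Section | Up to 30 days after last dose | Later |
|---|---|---|---|
| Serious events, expedited (by grade and hospitalization) | 10.4.1, footnote 1 | Whatever the attribution | Only if judged related |
| Deaths, expedited or as grade 5 events | 10.3.1, 10.5.3.3 | Whatever the attribution | Only if judged related |
| Grade 3-4 events on the CRF | 10.5.3.2 | Whatever the attribution | Whatever the attribution; no time limit stated |
| Grade 1-2 events on the CRF | 10.5.3.1 | Only if judged related | Only if judged related |
| Suspension-rule count, grade 3+ | 16.6.1 | Only if judged related | Only if judged related |
| Compared grade 3+ rate | 16.4.1.1 | Whatever the attribution | Whatever the attribution, except that later deaths enter as grade 5 only if judged related |

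Within the window, then, unblinding can affect whether grade 1-2 events are entered and what the suspension rule counts. After it, expedited reports of serious events and grade 5 submission are also exposed.

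**Suspension rule.** Section 16.6.1 re-reviews the attribution of grade 4 and 5 events called unrelated or unlikely. Grade 3 events are not covered. Accrual of 88 patients at 6 per month takes 88/6 = 14.7, stated as 15 months. A patient registered at the start finishes by day 70 at the latest, about 70/30.4 = 2.3 months. The code can thus be opened with about 15 - 2.3 = 12.7 months of accrual, and of the rule's operation, still to run.

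**Illustration only.** Let p be the chance that a placebo patient has a late event that a blinded physician would call related, and u the share of placebo patients unblinded. The documents give neither. With 26 evaluable placebo patients (16.2.1) and every such event losing its attribution, the expected number affected is 26 × p × u:
- p = 5%, u = 10%: 26 × 0.05 × 0.10 = 0.13
- p = 10%, u = 50%: 26 × 0.10 × 0.50 = 1.3
- p = 20%, u = 100%: 26 × 0.20 × 1.00 = 5.2

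Under Section 10.5.3.2, a grade 3-4 event among these would still be on the CRF; only its attribution would change.

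**The case against.** A reader might infer that late events in patients known to be on placebo disappear from the safety data and bias the safety comparison. The documents do not support that. Grade 3-4 events are submitted whatever their attribution, as are serious events and deaths within 30 days. The rate compared across arms is grade 3+ regardless of attribution. Its only written dependence on attribution is for deaths after 30 days, and survival follow-up records those anyway.

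The opposing case has further force:
- No adverse event query is scheduled after week 8, and the month-6 and month-12 calls do not include one. Late capture will be sparse in every arm, blinded or not.
- Unblinding is discretionary, and its frequency is unknown.
- Section 7.3.2 refers to the treating physician, while Section 10.0 makes the site principal investigator responsible for reporting. The documents do not say that the same person learns the arm and attributes the event.
- In the suspension rule's comparison of arms, losing placebo events favors suspension, which is the cautious direction and temporary.
- Waiting 30 days does nothing for reports that depend on attribution only after day 30.
- Off-study PEA bears only on exploratory recurrence and survival, and Appendix IX already asks about medication for CIPN.

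All of this stands, and it reduces the point to a modest one. It does not remove the gap: nothing requires attribution to be settled before the code is opened, and grade 3 attributions feeding the suspension rule are not re-reviewed.

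**Conclusion.** The point holds in limited form and is worth considering rather than essential. Section 7.3.2 permits knowledge of the arm before attribution is settled, which is out of step with the separation in Section 6.4.1. The exposure is confined to three items: grade 1-2 events in the descriptive summary; related grade 3+ events in the suspension rule, mainly grade 3; and serious-event reports and grade 5 submission after 30 days. The primary endpoint is unaffected, because the booklets must be mailed before the code is opened.

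The direction, toward a higher apparent PEA rate relative to placebo, assumes that whoever attributes the event knows the arm. The size cannot be derived from the documents. The range of 0.13 to 5.2 events rests entirely on assumed inputs. It is also tempting to quote an inflated PEA-to-placebo ratio of related late events, but that needs an assumed unblinding share, and the plan never analyzes such a ratio.

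**What to change.** In Section 7.3.2, permit a non-emergency code break only after all adverse events to date, including those from the week-8 call, have grade and attribution entered in Rave, and preferably only after the 30-day post-dose window has closed. Record the date of every code break. Have any later attribution made by someone who does not know the assignment, or flag it as unblinded; this covers the reports after 30 days that a waiting period cannot protect. On the existing Appendix IX medication question, record off-study PEA and its start date. Leave the emergency route in Section 7.3.1 unchanged.

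The cost is a short amendment to Section 7.3.2, a few form fields, and a blinded assessor or a flag for later attributions. Patients who want to know their assignment wait a little longer, up to about 30 days if the window condition is adopted.
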